## STUDY PROTOCOL

### Universe and Sample of the Study

Many studies have noted that the prevalence of pain in adults is generally high, and women in particular experience more pain (Damico et al., 2018; Dahlhamer et al., 2018; Ferrell et al., 2000; Larsson et al., 2017; Jackson et al., 2015; Woo et al., 2009). Therefore, the study population was chosen among female patients. The universe of the study consisted of 917 female patients aged 65 and over who attended the gynecology outpatient clinic of Training and Research Hospital in the four months from 1 August 2018. The sample consisted of 100 female patients who met the inclusion criteria and agreed to participate in the study.

### Inclusion Criteria

Patients aged 65 and over who scored 23 and above on the SMMSE, who did not have any disability preventing them from answering the questions, who were not addicted to alcohol or other substances, and who had no history of trauma in the previous six months, were included in the study.

### Data Collection and Management

The data of the study were collected using the Patient Identification Form prepared by the researchers, the GPM, and the SMMSE. The GPM is a 24-item multidimensional scale developed by Ferrell et al. (2000), for elderly individuals treated on an outpatient basis. Its validity and reliability in Turkish were confirmed by Dursun and Bektaş (2017). The Turkish version of the scale has five sub-dimensions: withdrawal due to pain (*Factor 1; Items 19, 20, 22, 23*); pain intensity (*Factor 2; Items 1, 2, 3, 4, 5, 6*); pain with movement (*Factor 3; Items 9, 10, 11, 12*); pain with strenuous activities (*Factor 4; Items 7, 8, 18, 21, 24*); and pain with other activities (*Factor 5; Items 13, 14, 15, 16, 17*). The total score is calculated by adding the "Yes" answers, and each item is multiplied by 2.38 and the total is converted into a score of between 0 and 100. Scores between 0 and 29 are considered to indicate mild pain, scores

between 30 and 69 are considered to indicate moderate pain, and scores of 70 and above are considered to indicate severe pain.

The SMMSE measures the degree of cognitive impairment. The SMMSE was validated in Turkish by Güngen, Ertan, Eker, & Yaşar (2002) in patients with mild dementia. The SMMSE consists of five parts: orientation, memory, attention/calculation, recall, language and motor function, and perception. Each question is worth 1 point. The maximum score obtainable is 30; a score of 24 to 30 points indicates normal cognitive function, a score of 18 to 23 points indicates mild dementia, while a score of 17 points or fewer indicates severe dementia. The threshold for the diagnosis of mild dementia in the Turkish population has been reported as 23/24 (Güngen et al., 2002).

There is no data security monitoring board in the study.

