#### **STATISTICAL ANALYSIS PLAN**

Data obtained from the study were processed and analyzed using SPSS 24 software. For the data determined to be abnormally distributed, the Mann-Whitney U test was used to compare two independent groups, and the Kruskal Wallis test was used to compare three or more independent groups. Spearman correlation coefficients were used to evaluate whether there was a linear relationship between variables. The Cronbach's alpha coefficient was calculated to determine the internal consistency of the scale. Statistical significance was accepted as  $p < 0.05$  (Christensen, Johnson, & Turner, 2015).

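### GPM scoring rule cannot reach its own 0–100 range: 24 items at one point per Yes, multiplied by 2.38, give at most 57.12

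*Combined protocol and SAP*

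**What the plan says.** All the scoring information is in Data Collection and Management. On size: "The GPM is a 24-item multidimensional scale". The section assigns the items to five factors, the first being "Items 19, 20, 22, 23". On the raw score: "The total score is calculated by adding the 'Yes' answers". On rescaling: "each item is multiplied by 2.38 and the total is converted into a score of between 0 and 100". On interpretation, the lowest band is "Scores between 0 and 29 are considered to indicate mild pain", moderate runs from 30 to 69, and "scores of 70 and above are considered to indicate severe pain".

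No response format or number of points is given for any GPM item. The one statement of points per question in that section concerns the SMMSE. The Statistical Analysis Plan adds no scoring rule. It lists the analyses: "the Mann-Whitney U test was used to compare two independent groups", Kruskal-Wallis for three or more groups, Spearman correlations, and a Cronbach's alpha whose "coefficient was calculated to determine the internal consistency of the scale".

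**The concern.** The item count, the rule of adding Yes answers, the multiplier, the stated range and the severe cut-off do not fit together if each Yes earns one point. The GPM is the only pain scale named, and the protocol turns its score into severity categories. An analyst who applied the rule literally would report scores compressed into roughly the lower 57% of the range and would classify nobody as having severe pain, however many items were endorsed.

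Whether the planned tests are also affected depends on which element is wrong:

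- **Wrong constant multiplier only.** Ranks are unchanged, so Mann-Whitney, Kruskal-Wallis and Spearman results stay as they are. Cronbach's alpha is also unchanged, because every item is scaled by the same constant. Only score levels and categories are wrong.
- **Extra points of multi-point items left out.** Item scores and the order of patients can change, so all of these results can change.

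**Working it through.** **Inputs, all from Data Collection and Management.** 24 items; total formed from Yes answers; multiplier 2.38; range 0 to 100; bands 0–29, 30–69, 70 and above.

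**1. Item count.** The factor lists hold 4 + 6 + 4 + 5 + 5 = 24 items, and items 1 to 24 each appear once. The count of 24 is confirmed.

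**2. Attempt to reproduce the stated upper limit of 100.** Maximum = items × points per Yes × multiplier = 24 × 1 × 2.38 = 57.12. The stated limit is not reproduced.

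**3. Raw points needed for the severe band.** 70 / 2.38 = 29.4, so 30 points are needed (29 × 2.38 = 69.02; 30 × 2.38 = 71.40). Only 24 are available.

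**4. What would restore the range.**
- Keeping 2.38: 100 / 2.38 = 42.02, so a raw maximum of 42 is needed (42 × 2.38 = 99.96). That is 42 − 24 = 18 points more than 24 one-point items supply, worth up to 18 × 2.38 = 42.84 score points per patient.
- Keeping 24 one-point items: the multiplier would have to be 100 / 24 = 4.17.

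**5. Raw totals falling in each band.**

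| Reading | Mild | Moderate | Severe | Maximum score |
|---|---|---|---|---|
| As written: 24 one-point items × 2.38 | 0–12 | 13–24 | none | 57.12 |
| Raw maximum 42 × 2.38 | 0–12 | 13–29 | 30–42 | 99.96 |
| 24 one-point items × 100/24 | 0–7 | 8–16 | 17–24 | 100 |

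As written, 12 Yes answers score 28.56 and 13 score 30.94. Under the third reading they would score 50.00 and 54.17. So if all 24 items really are yes/no, patients with 8–12 Yes answers would be recorded as mild instead of moderate, and those with 17–24 as moderate instead of severe. The net change in the size of the moderate group cannot be known from the documents.

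Two raw totals fall between printed bands: 29 on the 42-point reading (69.02), and 7 on the 24-point reading with 100/24 (7 × 100/24 = 29.17). The table places each in the lower of the two bands.

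**6. Can the order of patients change?** Suppose *k* multi-point items share the 18 extra points. Patient A has 13 Yes answers, all on one-point items (this needs 24 − *k* ≥ 13). Patient B has 12, including every multi-point item at its maximum (this needs *k* ≤ 12). Both are possible for *k* = 1 to 11.

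| | As written | Raw maximum 42 |
|---|---|---|
| A | 13 × 2.38 = 30.94, moderate | 13 × 2.38 = 30.94, moderate |
| B | 12 × 2.38 = 28.56, mild | (12 + 18) × 2.38 = 71.40, severe |

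The order reverses. This is a constructed extreme that shows rank changes are possible; it does not estimate how often they occur.

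**The case against.** The best defence is that the rule is abbreviated rather than wrong. The multiplier is 100/42 to two decimals, and the 0–100 range and the cut-off of 70 both suit a 42-point total, so three printed elements agree and only the phrase about Yes answers is out of line. The protocol never says that a GPM item is worth one point. It also presents the GPM as an existing scale with a cited Turkish validation, so the investigators may well have scored it correctly. On this view the defect is one of description. The Statistical Analysis Plan names no analysis of the severity categories, and harm to the tests it does name needs the further assumption that multi-point answers were collapsed to a single point.

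Much of this stands. The 42-point reading is the more likely one, the 100/24 reading requires the printed multiplier to be wrong, and no scoring error in the data has been shown. The figure of 57.12 also assumes that every item can be answered Yes; if some cannot, the literal maximum is lower still.

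But the defence concedes that the written rule omits 18 of 42 raw points. The protocol chose to state a scoring rule, and that rule cannot produce its own range or its top category. Reading the conversion to 0–100 as a further rescaling step does not help either: no such step is given, and it would make 2.38 redundant.

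**Conclusion.** The concern holds. At one point per Yes, the stated rule falls 100 − 57.12 = 42.88 points short of its stated maximum and leaves the severe category empty. The arithmetic is exact, and its only condition is the one-point reading.

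Which element is at fault is not settled by the documents; omitted points on multi-point items are the likelier explanation. The effect on reported results is unknown, because the scoring actually used is not shown. Score levels and categories are wrong if the text was followed. The rank tests, correlations and alpha are at risk only if multi-point items were counted simply as Yes. This should be corrected, because scores on the study's only named pain scale cannot be reproduced from the text.

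**What to change.** 1. Check the GPM form that was used. Rewrite the rule with each item's response format and points, the raw maximum, and a multiplier equal to 100 divided by that maximum: 2.38 if the raw maximum is 42, 4.17 if there are 24 one-point items.
2. Check the derived-score syntax and the attainable maximum in the data set against the corrected rule. Recompute scores and categories if they differ.
3. If multi-point items were counted only as Yes, also re-run the Mann-Whitney and Kruskal-Wallis tests, the Spearman correlations and Cronbach's alpha.
4. State how non-integer scores are banded, so that values such as 69.02 or 29.17 have a defined category.

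The cost is one or two sentences in the scoring section and a syntax check. Re-analysis is needed only if the check finds a difference, and no new data have to be collected.

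### Does placing a GPM total of 0 in the mild-pain band, when pain is not an entry criterion, distort the analysis?

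*Combined protocol and SAP*

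**What the plan says.** Under Data Collection and Management, the protocol describes the GPM as a 24-item scale and gives the scoring rule: "each item is multiplied by 2.38 and the total is converted into a score of between 0 and 100". Zero is therefore an admissible total. Three severity bands follow. The lowest is defined by "Scores between 0 and 29 are considered to indicate mild pain"; the rest of the scale is split as "between 30 and 69 are considered to indicate moderate pain, and scores of 70 and above are considered to indicate severe pain". No class lies below mild.

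The Inclusion Criteria require age 65 or over and an SMMSE score of at least 23, and then admit women "who did not have any disability preventing them from answering the questions, who were not addicted to alcohol or other substances". A final condition, on recent injury, closes the list. Current pain is not on it. The women come from gynecology outpatient attenders, and the Universe and Sample section gives the size: "The sample consisted of 100 female patients who met the inclusion criteria and agreed to participate in the study".

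The Statistical Analysis Plan names the Mann-Whitney U test, the Kruskal Wallis test, Cronbach's alpha and a correlation analysis ("Spearman correlation coefficients were used to evaluate whether there was a linear relationship between variables"). It does not mention the severity bands.

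**The concern.** A scale whose lowest class is mild pain, used in women who need not have pain, has nowhere to put a woman who reports none. Followed to the letter, the rule calls a total of 0 mild pain.

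Two reporting consequences would follow. A severity table would mix women scoring 0 with women who have low but real pain scores. And if a proportion with any pain were taken from band membership, it would approach 100% whatever the women answered, because every band is a pain class. The protocol justifies its choice of population by saying that "the prevalence of pain in adults is generally high, and women in particular experience more pain", so a reader might well look for such a proportion. One extra table row would settle the matter, which makes a change look cheap.

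**Working it through.** There is no sample size, power or error-rate figure to reproduce here. The check applies the stated rule and then asks which planned results depend on it.

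**Inputs.** Bands 0–29, 30–69, and 70 and above; multiplier 2.38; range 0 to 100; 24 items (all from Data Collection and Management). Sample size 100 (Universe and Sample of the Study). Named methods (Statistical Analysis Plan). The number of women scoring 0, written *k*, is given nowhere.

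**Step 1: where a zero falls.** 0 × 2.38 = 0.00, which lies in 0–29 and so is mild. The literal reading holds.

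**Step 2: size, if the bands were tabulated.** The zero scorers' share of the mild row, in percentage points, is 100 × *k*/100 = *k*. The share scoring above 0 is (100 − *k*)/100.

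| *k* (assumed) | Points in the mild row from zero scorers | Share scoring above 0 |
|---|---|---|
| 0 | 0 | 100% |
| 1 | 1 | 99% |
| 5 | 5 | 95% |
| 10 | 10 | 90% |

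If the underlying share of zero scorers were 1%, the chance of at least one among 100 women would be 1 − 0.99^100 = 63%; at 5% it would be 1 − 0.95^100 = 99%. These shares are assumptions too. The protocol's remark on high pain prevalence points towards a small *k* without excluding zeros.

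**Step 3: whether all 100 women must receive a pain label.** Only under a rounding rule that the documents do not state. Reaching 100 takes 100/2.38 = 42.02, or about 42 raw points. If raw totals are whole numbers up to 42 (assumption), then 28 × 2.38 = 66.64 is moderate, 30 × 2.38 = 71.40 is severe, but 29 × 2.38 = 69.02 falls between 69 and 70 and belongs to no stated band. The lower edge causes no such trouble: 12 × 2.38 = 28.56 and 13 × 2.38 = 30.94. A statement that 100 of 100 women are labelled with pain therefore holds only if scores are rounded to whole numbers.

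**Step 4: what a total of 0 means.** If the total counts only Yes answers, its maximum is 24 × 2.38 = 57.12, short of 100. Some items must score in another way, or the scoring sentence is incomplete. The text does not settle this, so a row headed as no pain would claim more than the documents support.

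**Step 5: dependence of the planned analyses on the band label.**
- Mann-Whitney U and Kruskal Wallis on the GPM score use ranks. Renaming the class of a zero score leaves the score and its rank as they were, so the statistics and p-values are identical.
- Spearman's coefficient also uses ranks and is identical.
- Cronbach's alpha is computed from item responses and is identical.

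No named analysis of scores or items changes for any value of *k*.

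**The case for a change.** The best case for acting is that the bands are defined for some purpose, and the evident one is to describe severity. The Statistical Analysis Plan does not list its grouping variables, so a table by band, or a three-group Kruskal Wallis comparison by band, cannot be ruled out. In such a table women scoring 0 would be invisible, and the reader could not even tell whether there were any. A separate row costs nothing in data collection and could sit beside the stated bands.

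Part of this stands. If bands are reported, an any-pain proportion should not be read from them, and a count at a total of 0 would be informative. But that rests on conditions the documents do not supply: that the bands are tabulated or used as groups, and that at least one woman scored 0. The distorted prevalence needs a third, that someone treats band membership as the presence of pain. Nothing in the plan proposes this.

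It also matters that the bands stand in the paragraph describing the instrument and its Turkish validation and read as the scale's own labels. Whether they match the published cut-offs cannot be checked from the documents. If they do, using them as given is ordinary practice and keeps results comparable with other users of the scale; nothing in the text suggests that they do not.

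**Conclusion.** The observation is accurate: a total of 0 is inside the mild band, no band lies below it, and pain is not required for entry. It is not an error in a planned analysis. No method named in the Statistical Analysis Plan depends on the label when it is applied to scores or items, so the effect on those results is exactly nil for any number of zero scorers. For a table by band, which the plan does not call for, the effect would be 1 percentage point of the mild row per zero scorer, with the number of such women unknown and possibly none.

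The conclusion assumes that the bands serve as a description of the instrument, as their placement suggests. If the investigators do tabulate severity, the zero totals are in the data. An analyst can note their count under a neutral label beside the stated bands, and avoid inferring any-pain prevalence from band membership, without an amendment. A revised set of bands would depart from the plan's own labels and improve no result that the plan commits to.

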#### **STATISTICAL ANALYSIS PLAN**

Data obtained from the study were processed and analyzed using SPSS 24 software. For the data determined to be abnormally distributed, the Mann-Whitney U test was used to compare two independent groups, and the Kruskal Wallis test was used to compare three or more independent groups. Spearman correlation coefficients were used to evaluate whether there was a linear relationship between variables. The Cronbach's alpha coefficient was calculated to determine the internal consistency of the scale. Statistical significance was accepted as  $p < 0.05$  (Christensen, Johnson, & Turner, 2015).

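### The SAP specifies no estimate of the size of a group difference and no confidence interval for any result; separately, the GPM scoring rule as written does not reach its own 0-100 range

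*Combined protocol and SAP*

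**What the plan says.** The Statistical Analysis Plan is a single paragraph. Its rank tests are conditional, the condition being worded as "For the data determined to be abnormally distributed". Where there are two groups, it states that "the Mann-Whitney U test was used to compare two independent groups". Where there are more than two, it states instead that "the Kruskal Wallis test was used to compare three or more independent groups". No method is named for data judged normal. The decision rule is p < 0.05. For association, "Spearman correlation coefficients were used to evaluate whether there was a linear relationship between variables". Cronbach's alpha is to be calculated for internal consistency. Neither this paragraph nor the protocol sections before it mention a median difference, a shift estimate, a probability of a higher score, a rank-based effect size or a confidence interval.

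On sample size, Universe and Sample of the Study says "The sample consisted of 100 female patients who met the inclusion criteria and agreed to participate in the study". It gives no power, target difference, standard deviation or group sizes.

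On the score, Data Collection and Management says "The GPM is a 24-item multidimensional scale". The total is built from the 'Yes' answers, after which "each item is multiplied by 2.38 and the total is converted into a score of between 0 and 100". Of the three pain bands, the top one is defined by "scores of 70 and above are considered to indicate severe pain".

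**The concern.** A rank test answers whether two groups differ more than chance would explain. It does not say by how much, or how well the data pin that down. Here there is no planned power against which a null result could be read, so only an interval can show whether a non-significant comparison rules out a worthwhile difference or merely fails to detect one. The reverse also holds: a p-value just under 0.05 does not show whether the difference is trivial or large. If the report follows the SAP and adds nothing, non-significant comparisons are likely to be read as evidence of no difference.

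The scoring text is a separate matter that becomes important once sizes are reported. A difference in GPM points can be interpreted only if the reader knows what range the points cover, and the described arithmetic does not produce the stated range.

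**Working it through.** The documents give no power calculation or effect size, so there is no figure of the plan's own to reproduce. The checks below show what intervals would reveal at this sample size.

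**Inputs.** N = 100, from Universe and Sample of the Study. The significance level of 0.05 is from the SAP; it is taken as two-sided, since the SAP does not say. The group splits are my assumptions, because the documents give none: 50/50 and 80/20. The 24 items, the multiplier 2.38, the 0-100 range and the band at 70 are from Data Collection and Management.

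**1. Two-group comparison, without assuming a score range or SD.** Let P be the probability that a woman in one group scores higher than a woman in the other. With no true difference and no ties, its standard error is sqrt((n1 + n2 + 1) / (12 × n1 × n2)).

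- 50/50: sqrt(101 / (12 × 2,500)) = sqrt(101 / 30,000) = 0.0580; × 1.96 = 0.114. The interval is about 0.39 to 0.61.
- 80/20: sqrt(101 / (12 × 1,600)) = sqrt(101 / 19,200) = 0.0725; × 1.96 = 0.142. The interval is about 0.36 to 0.64.

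Simulation at true values of P from 0.56 to 0.64 gives the same half-widths, ± 0.11 and ± 0.14, so the formula serves slightly away from the null as well. Two examples at 50/50 follow:

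- An observed P of 0.56 is not significant, yet its interval runs from about 0.45 to 0.67 (0.56 ± 0.11).
- An observed P of 0.614 is just at p = 0.05, and its interval runs from about 0.50 to 0.72 (0.614 ± 0.11).

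The p-value alone conveys neither range. A more uneven split is worse: at 90/10 the half-width is 1.96 × sqrt(101 / (12 × 900)) = 0.19.

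**2. Spearman coefficient.** On the Fisher z scale with variance (1 + r²/2) / (n - 3) and n = 100:

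- r = 0.10: z = 0.1003; SE = sqrt(1.005 / 97) = 0.1018; limits on the z scale -0.099 and 0.300; back-transformed, -0.10 to 0.29.
- r = 0.30: z = 0.3095; SE = sqrt(1.045 / 97) = 0.1038; limits on the z scale 0.106 and 0.513; back-transformed, 0.11 to 0.47.

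**3. GPM scoring.**

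- The five sub-dimensions list 4 + 6 + 4 + 5 + 5 = 24 items, which agrees with the stated number.
- Read literally, one point per 'Yes' gives a maximum of 24 × 2.38 = 57.12.
- Reaching 100 needs 100 / 2.38 = 42.0 raw points (42 × 2.38 = 99.96).
- Reaching 70 needs 70 / 2.38 = 29.4 raw points, more than the 24 available.

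Under the literal rule, then, neither the top of the range nor the severe band can be reached. The section does not explain where 42 raw points would come from.

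**The case against.** The strongest reply is that silence is not a decision. The SAP paragraph lists tests; it also leaves out medians, counts and all descriptive statistics, and nowhere says that p-values will stand alone. A reader might infer that the report will contain bare p-values. The documents do not support that. What stands is narrower: estimates and intervals are not specified, so nothing commits the study to them.

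On scoring, a reader might infer that no score range is given, or that the scores were wrongly computed. Neither follows. A 0-100 range is stated; it is the described arithmetic that does not fit it. The 57.1 ceiling holds only if every item counts 0 or 1, and the section does not give the items' response formats, including those of the six pain-intensity items. An incomplete description is as plausible as a wrong score. Nor does the multiplier affect the tests: rank tests, P and Spearman coefficients are unchanged by a constant factor, although they would change if some items carry more than one raw point and were not scored that way. The scoring point is therefore separate from the reporting point.

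Three other stronger readings also fail:

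- That the rank tests are wrong: they are valid for unadjusted comparisons.
- That lack of covariate adjustment is a fault: the text states no aim of establishing independent associations.
- That the plan has a multiplicity error after Kruskal-Wallis: it plans no pairwise comparisons.

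Finally, the group splits are assumed, and the SAP is written in the past tense, which suggests that the analysis is already done. Both limit what can be claimed; neither removes the gap.

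**Conclusion.** The concern holds as an omission that should be repaired. The SAP names tests and a threshold for group comparisons but no measure of the size of a difference, and it plans no interval for any result. At N = 100 the missing information is not small: ± 0.11 to ± 0.14 around 0.50 for the probability of a higher score, and roughly ± 0.20 around a weak Spearman coefficient. The first pair of figures rests on the assumed 50/50 and 80/20 splits, no ties and no true difference; the second uses the Fisher approximation. No magnitude in GPM points is offered, because the documents give no SD and do not say which outcomes and groups are compared.

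Separately, the scoring rule read literally is inconsistent with the stated range and with the severe band. Whether the description or the scoring is at fault cannot be settled from the documents.

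**What to change.** 1. Beside each Mann-Whitney p-value, report one effect estimate with its 95% confidence interval: the Hodges-Lehmann difference, or the probability of a higher score where the two distributions differ in shape.
2. If pairwise differences are shown after Kruskal-Wallis, give them with intervals. Adjust these for multiplicity if they are shown whatever the Kruskal-Wallis result (for example Bonferroni, which for three groups means 1 - 0.05/3 = 98.3% each).
3. Report 95% confidence intervals for the Spearman coefficients.
4. Reconcile the GPM scoring text: item response formats, raw maximum, multiplier and bands. Confirm that the scores analysed follow the reconciled rule before giving any difference in points.
5. Label the results as unadjusted. If the analysis is already done, label the added intervals as not pre-specified.

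The cost is SAP wording and a little more analysis of data already collected. The intervals will be wide and will make the results look less definite. The Hodges-Lehmann difference reads as a shift only when the groups have similar distribution shapes, which is why item 1 offers the alternative.

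### Does calling Spearman's coefficient a check for a linear relationship require a change to the SAP?

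*Combined protocol and SAP*

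**What the plan says.** The correlation analysis is specified in one sentence of the Statistical Analysis Plan: "Spearman correlation coefficients were used to evaluate whether there was a linear relationship between variables". The variables to be correlated are not named.

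The same section sets rank-based methods for group comparisons: "For the data determined to be abnormally distributed, the Mann-Whitney U test was used to compare two independent groups", with Kruskal-Wallis for three or more groups. Cronbach's alpha is planned for internal consistency, and the significance threshold is p < 0.05. No Pearson coefficient, regression or scatterplot is mentioned.

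The data come from one sample: "The sample consisted of 100 female patients who met the inclusion criteria and agreed to participate in the study" (Universe and Sample of the Study). For the pain scale, the geriatric pain measure (GPM), "the total is converted into a score of between 0 and 100" (Data Collection and Management).

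**The concern.** The stated purpose and the statistic do not match. Rho is Pearson's coefficient applied to ranks. It is linear in the ranks only, whereas the sentence speaks of linearity between the variables themselves. Any strictly increasing transformation of either variable leaves rho unchanged, so it cannot distinguish a straight line from a monotonic curve.

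Taken literally, the sentence would let an author report a significant rho as evidence of a straight-line relationship, for instance between age and pain score, and a reader might infer a constant change in pain per year of age. The analysis could not support that, and nothing else in the plan would supply the missing evidence. (The pair is only an example, since the plan names none.)

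**Working it through.** The plan gives no figure to reproduce on this point. The check asks whether the property is as described, and whether anything in the study depends on the word.

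**Inputs.** n = 100 (Universe and Sample of the Study); alpha = 0.05, sidedness not stated, two-sided assumed (Statistical Analysis Plan). The curve shapes below are assumed for illustration and are not estimates for this study.

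**1. The definition.** Without ties, rho = 1 − 6Σd² / [n(n² − 1)], where d is the difference between a patient's two ranks. If y is strictly increasing in x, every d is 0. With n = 100, rho = 1 − 6 × 0 / (100 × 9,999) = 1, whatever the curvature.

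**2. Size of the mismatch on assumed curves.** For 100 noise-free points, x equally spaced from 0 to 1 (R² is r squared before rounding):

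| Curve | rho | Pearson r | Straight-line R² |
|---|---|---|---|
| x² | 1.00 | 0.968 | 0.936 |
| square root of x | 1.00 | 0.977 | 0.954 |
| logistic, slope 10 | 1.00 | 0.973 | 0.947 |
| exp(3x) | 1.00 | 0.935 | 0.874 |
| exp(5x) | 1.00 | 0.856 | 0.733 |
| x¹⁰ | 1.00 | 0.660 | 0.436 |

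The literal claim is therefore wrong. With mild curvature (the first three rows) a straight line still explains about 94% to 95% of the variance, so the word would hardly mislead. Only extreme shapes open a wide gap, and nothing in the documents suggests such shapes here.

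**3. What the word changes in the analysis.** Using the usual t approximation with 98 degrees of freedom, t = 1.984 and the critical absolute rho is t / √(n − 2 + t²) = 1.984 / √(98 + 3.938) = 0.197. This depends on n and alpha alone. Rho, its p-value and the threshold are the same whichever adjective describes them.

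**4. Whether the risk belongs to Spearman.** The same threshold applies to Pearson's r. For x¹⁰, r = 0.660 is well above 0.197, so a Pearson test would also be significant for a curve on which a straight line explains only 44% of the variance. A significant coefficient of either kind does not establish shape.

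**5. Whether Spearman is the wrong choice.** In 100 simulated pairs with a skewed outcome, rho was 0.364 both before and after taking logs of that outcome, while Pearson's r moved from 0.03 to 0.37. That stability suits the non-normal data for which the plan chooses its other rank tests.

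**6. Whether anything depends on linearity.** The sections on sample, inclusion criteria, data collection and analysis contain no hypothesis about linearity, no slope to estimate, no prediction model and no decision that turns on the shape of a relationship. The plan gives a purpose and a p-value threshold, but no rule on what a significant coefficient may be said to show.

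**The case for a change.** The strongest case for a change is that the statement is wrong by definition, without any assumption about the data, and that an analysis plan is where the meaning of a result is fixed. If linearity was intended, the plan has no method for it; if it was not, the purpose is misdescribed. Replacing one word costs almost nothing.

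The first part stands: the adjective is incorrect, and no other sentence corrects it. The rest does not amount to a need for change. The dilemma has force only if linearity matters to some aim of the study, and none is stated; the natural reading is loose wording for correlation. The harm needs a later report that claims a straight line, and the documents contain no results or conclusions to correct. Low cost is not a gain in itself. Adding scatterplots or a regression with a curvature check would answer a question the study does not ask.

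**Conclusion.** The wording is inaccurate, but no change to the plan follows. The method suits the data as the plan describes them, and the effect of the slip on every coefficient, p-value, threshold and sample size is zero. An analyst following the plan will compute Spearman's rho, and a statistically informed reader will take it as rank association whatever adjective introduces it.

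This rests on two conditions: that no unstated aim concerns linearity, and that the report describes a significant rho as an association and not as a straight-line relationship. Because the variable pairs are unnamed, how far any real pair departs from linearity cannot be judged from the documents. The curves above show the property only. The 0.197 threshold assumes a two-sided test, but it is unaffected by the wording under either sidedness.
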